### 3. Focus of the Study and Specific Aims

#### ***BLUE CORAL and LIFT COVID study designs (Figure)***

**LIFT COVID** is a 300-participant, two-arm, parallel groups RCT with 6-month follow up nested within the NHLBI PETAL Network's **BLUE CORAL** observational study of patients hospitalized with cardiorespiratory manifestations of COVID-19. The PETAL data coordinating site, the University of Michigan, will screen participants, conduct informed consent, and conduct all follow up interviews. Participants with symptoms of depression (PHQ-9  $\geq 5$ ) 1 month after hospital discharge will be randomized to either the LIFT intervention (Standard Dose, App-based Symptom Response, No intro

Call) or usual care control. Follow up interviews will be done 1, 3, and 6 months post-discharge (i.e., 0, 2, and 5 months post-randomization), as per BLUE CORAL's current timeline.

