## 5. Previous enrollment in BLUE CORAL

### **4.b. LIFT COVID eligibility**

There will be 300 BLUE CORAL patients selected for detailed post-hospital assessment—these will be the target population for the LIFT COVID RCT. If there are more eligible patients, patients may be selected randomly or according to enrichment strategies which will be informed by the composition of the cohort. Informed consent will be obtained by telephone for these potential participants.

Inclusion criteria:

1. Enrolled in BLUE CORAL
2. Survival to hospital discharge
2. English-speaking
3. Domiciled with access to a working telephone and smartphone, tablet, or computer with wifi or internet connection
4. Absence of severe dementia or severe functional disability before hospitalization or at time of 1 month post-discharge interview

Exclusion criteria:

1. PHQ-9 <5 at time of interview 1 month post-discharge
2. Suicidal ideation at time of interview 1 month post-discharge

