### 7.b. LIFT COVID Surveys

As shown in Table 1, participants enrolled in the LIFT COVID intervention arm will also complete the PHQ-9 survey weekly within the LIFT mobile app for the duration of the 4-week intervention.

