**Step 4: intervention.** Intervention participants receive Lift app access. After T3 (6 month post-discharge) BLUE CORAL survey, traditional care control participants can access Lift if they wish via an email automatically sent from the LIFT platform.

Pro00106306: Addressing psychological distress symptoms among serious illness survivors of a viral pandemic with a completely self-directed, symptom-responsive mobile mindfulness intervention

and activation with the unique ID, the participant's experience will be automated.

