In this trial, we expect AEs to be extremely uncommon because it is a behavioral trial. However, it is possible that participants could become distressed in an ICU setting in the event that their loved one dies or becomes more ill. One particular symptom of note that will be considered an AE and reported to the IMC will be suicidal ideation as operationalized by responding to PHQ-9 item #9 (Thoughts that you would be better off dead or of hurting yourself in some way) with either 'more than half the days' or 'nearly every day' out of the preceding 2 weeks. In this trial, we do not anticipate any SAEs because it is a behavioral trial. A SAE in this trial would include a suicide attempt, a hospitalization, or death. All serious adverse events will be reported within the standard timelines required to these bodies as well as to the OHRP and the NIH/NCCIH. AEs and SAEs will be reported to these agencies per their standard guidelines.

While we do not anticipate any UPs because it is a behavioral trial that focuses on ICU patients, critical illness and its recovery process are unpredictable. Unanticipated problems will be identified, discussed by the PIs, and resolved by group consensus. Therefore, should there be unanticipated problems observed we propose the following reporting process—itself framed by NIH guidelines. First, the PIs and Duke University will include a written report that will be submitted to the NCCIH, the study DSMB, and the Central IRB that will describe the UP, the context, and the proposed corrective plan. This written report will be provided within 1 week (unless it/they is/are also an SAE, in which case the timeline for SAE reporting will be followed). The UP will also be forwarded OHRP using [[contact]](mailto:[contact]) within two weeks of the event.

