#### Period and Frequency for Event Assessment and Follow-Up

Unanticipated problems will be recorded in the data collection system throughout the study.

The PI will record all reportable events with start dates occurring any time after informed consent is obtained until 7 (for non-serious AEs) or 30 days (for SAEs) after the last day of study participation. At each study visit, the investigator will inquire about the occurrence of AE/SAEs since the last visit. Events will be followed for outcome information until resolution or stabilization.

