The main responsibilities of the DSMB will be to (a) assess for the presence of potential harms and unintended consequences of the LIFT intervention, (b) ensure the validity and integrity of the data, and (c) make recommendations to the investigators and to the NIH about whether the study should be continued without modification, continued with modification, or terminated.

The initial DSMB meeting will occur before the initiation of subject enrollment for the purpose of updating members on the study, ensuring agreement on the review process, establishing the review methodology and procedures, ensuring all conflicts of interest are disclosed (to be reviewed by NCCIH staff), reviewing the protocol, and codifying a written charter. The NCCIH's Data Safety Monitoring Plan (DSMP) Template will be used to guide the drafting of the charter. This document will specify procedures for protocol amendments, ensuring participant confidentiality and privacy, ensuring database protection, coordinating center responsibilities, creating adverse outcome definitions (adverse events, unanticipated problems, and serious adverse events), protocol for reporting and responding to adverse events while also maintaining subject confidentiality, justifying sample size, assessing accrual and compliance, halting and stopping rules (drafted with the assistance of the DSMB chair and the DSMB lead statistician), approving informed consent documents, and guidelines for quality control and quality assurance. Before enrollment begins, the DSMB charter will be approved by both the DSMB and the NCCIH; additionally, ClinicalTrials.gov registration will be finalized as per the Milestone Plan shown in the Research Strategy document.

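### Minor: for a non-zero PHQ-9 item 9 answer without intent, Section 15 tells the team both to do nothing and to call; secondarily, this adverse event is looked for up to six times in LIFT and twice in control.

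*Combined protocol and SAP*

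**What the plan says.** **Definition.** The adverse event text in Section 15 states "In this trial, we expect AEs to be extremely uncommon because it is a behavioral trial", then names a single symptom that "will be considered an AE and reported to the IMC will be suicidal ideation as operationalized by responding to PHQ-9 item #9" with one of the two most frequent response options (scores 2 and 3).

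**Response to an item 9 answer.** Two places in Section 15 deal with it.
- The Suicidality Response Plan (point 6 of the participant oversight plans) has a two-step app check: PHQ-9 item 9, then a suicidal intent question. If item 9 is 1, 2 or 3 and intent is yes, the app alerts staff, who contact the participant at once. If intent is no, both the app action and the team action are n/a.
- Reporting Procedures treats the item 9 symptom as one for which staff will telephone the participant, judge how serious the situation is and triage to psychiatric support. It sets no intent condition.

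**When item 9 is asked.** Section 3: "Follow up interviews will be done 1, 3, and 6 months post-discharge (i.e., 0, 2, and 5 months post-randomization"). Section 4.b lists as an exclusion "Suicidal ideation at time of interview 1 month post-discharge". Section 7.b adds that "participants enrolled in the LIFT COVID intervention arm will also complete the PHQ-9 survey weekly within the LIFT mobile app for the duration" of the four-week program. Under Section 8, Step 4, it is only after the 6-month survey that "traditional care control participants can access Lift if they wish via an email automatically sent from the LIFT platform".

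**Other safety collection.** "At each study visit, the investigator will inquire about the occurrence of AE/SAEs since the last visit" (Section 15, Period and Frequency for Event Assessment and Follow-Up). Section 17 makes adverse event reports and PHQ-9 scores the DSMB's primary safety measures. It allows formal tests, including of adverse event rates between groups, if they are requested and under DSMB supervision. It leaves to the DSMB charter tasks such as "creating adverse outcome definitions (adverse events, unanticipated problems, and serious adverse events").

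**The concern.** The main difficulty is operational. A LIFT participant may report in the app thoughts of death or self-harm on most days and deny intent. By definition that answer is an adverse event to be reported. Someone working from the table would take no further step; someone working from Reporting Procedures would telephone. Two staff members could each follow the protocol and act differently on the same safety answer.

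The secondary difficulty is one of interpretation. The named event is defined by a questionnaire answer, so it is captured mainly when the questionnaire is given, and LIFT is asked more often. With very few events expected, someone reading raw counts by arm could take more frequent asking for more harm.

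**Working it through.** **1. The two instructions side by side**

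| Item 9 | Intent | Suicidality Response Plan table: team action | Reporting Procedures: team action | Named adverse event? |
|---|---|---|---|---|
| 0 | not asked | n/a | none | no |
| 1 | no | n/a | call and assess | no |
| 2 or 3 | no | n/a | call and assess | yes |
| 1, 2 or 3 | yes | contact at once | call and assess | yes if 2 or 3 |

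The conflict is confined to the two rows with intent no. Reporting Procedures does not say which non-zero scores trigger the call. The table above takes it as any of them. If only scores 2 and 3 were meant, the conflict would remain in exactly the row that is also an adverse event.

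Three other passages could have settled the matter:
- Point 4 of the oversight plans promises an information sheet for passive ideation.
- The text after the response plan promises Lifeline details for anyone deemed not actively suicidal.
- Section 17 has the Study Manager watch the safety system linked to the weekly PHQ-9s as a second check.

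None of them says whether staff call when intent is no.

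**2. Post-randomization chances to record the event**

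- LIFT: 4 weekly in-app surveys + 3-month + 6-month = up to 6.
- Control: 3-month + 6-month = 2.
- The 1-month PHQ-9 counts for neither arm. It is the pre-randomization baseline, and suicidal ideation at that interview is an exclusion.

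**3. Size of the lean under equal true risk**

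The plan states no item 9 rate, so there is no figure of its own to reproduce. Assumptions: 150 per arm, all surveys completed, one count per participant, and a chance q per survey of 0.25% or 0.5%, chosen to represent events expected to be very rare.

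Expected participants flagged in k surveys:
- Independent answers: 150 × [1 − (1 − q)^k].
- Answers with within-person correlation ρ (beta-binomial): with s = (1 − ρ)/ρ and b = s(1 − q), 150 × [1 − ∏ (b + j)/(s + j)], j = 0 to k − 1.

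Example, q = 0.5% and independent answers: 150 × (1 − 0.995^6) = 4.44 against 150 × (1 − 0.995^2) = 1.50.

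The last column is the chance that a two-sided Fisher test gives p < 0.05 with LIFT higher, by exact enumeration.

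| q | ρ | LIFT | Control | Ratio | Excess | False signal |
|---|---|---|---|---|---|---|
| 0.25% | 0 | 2.24 | 0.75 | 2.99 | 1.49 | 1.3% |
| 0.25% | 0.5 | 0.92 | 0.56 | 1.63 | 0.35 | 0.02% |
| 0.25% | 0.8 | 0.56 | 0.45 | 1.24 | 0.11 | 0.0% |
| 0.5% | 0 | 4.44 | 1.50 | 2.97 | 2.95 | 9.4% |
| 0.5% | 0.5 | 1.83 | 1.12 | 1.63 | 0.71 | 0.4% |
| 0.5% | 0.8 | 1.12 | 0.90 | 1.24 | 0.22 | 0.04% |

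Sensitivity:
- Correlation of 0.8 placed on a latent normal scale, a weaker dependence between answers, gives 2.48 against 1.25 at q = 0.5%: an excess of 1.23 and a false-signal chance of 1.3%.
- At q = 1% with ρ = 0.5 to 0.8, the excess is 1.40 to 0.44 and the false-signal chance 2.5% to 0.5%.
- If 60% of app surveys are completed, at q = 0.25-0.5% the ratio is 1.17 to 2.19 and the excess at most 1.77, the top values under independence.
- Nominal significance needs at least 6 against 0, 8 against 1 or 10 against 2 participants.

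**4. After restriction to the common interviews**

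The count becomes 2 against 2 and the expected ratio under equal risk is 1.0. The false-signal chance in this direction is at most 0.1% at q = 0.25-0.5%.

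**The case against.** **On the conflicting instructions.** The table describes only the app's automatic alert for active intent, which is one of two routes into the response plan; staff concern is the other. Reporting Procedures can be read as a staff layer added on top. That reading is fair, and it is probably what the sponsor intends. It does not explain a team-action column that reads n/a, and no passage states it. A reader might go further and infer that participants with ideation but no intent are left unattended. The documents do not support that: an information sheet, Lifeline details in both arms and the Study Manager's second check are all provided.

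**On the unequal counts.** The weekly PHQ-9 is part of the intervention, since Section 9 uses it to steer the app's response to non-responders. Reporting Procedures openly acknowledges that symptoms will be known weekly in that arm. Any lean is toward over-detecting harm, the cautious direction. The inquiry about adverse events at each visit covers both arms, although it does not apply the item 9 threshold to the weeks in which controls complete no PHQ-9. These points stand and keep this part small.

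A reader might infer that the planned safety analysis is biased, or that LIFT could be stopped on a false signal. The documents do not support that either. No between-arm adverse event test is planned. The stopping language in Section 17 concerns a significant rise in PHQ-9 score. The charter, which may set definitions and review methods that deal with this, is not among the documents. The 9.4% false-signal figure requires independent answers, which is implausible when the same person is asked weekly about the preceding two weeks.

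**Conclusion.** The conflict between the response plan table and Reporting Procedures is an error as written. It is minor, confined to a non-zero item 9 answer with intent no, and rests on no assumed rate.

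The unequal number of surveys is a correct observation but supports only a cheap improvement in presentation. The expected excess in LIFT is under one participant if the rate is 0.25-0.5% per survey and answers are correlated 0.5-0.8. Under weaker dependence it is one to three participants at the upper rate. Both the rate and the correlation are assumptions; the documents give neither. The efficacy analysis is unaffected.

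**What to change.** 1. In the Suicidality Response Plan table, replace the n/a team action for item 9 non-zero with intent no by the call-and-assess step in Reporting Procedures, so that the same answer always leads to the same action. This costs one table cell and no new work, because the calls are already promised.

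2. In the adverse event or DSMB text, or in the charter if it does not already say so, add two or three sentences. Any between-arm comparison of this event should use item 9 at the common 3- and 6-month interviews, with one count per participant, shown beside a LIFT-only listing of app-detected events. Those events are still acted on and reported as now.

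The second change has a cost that should be stated with it. The program lasts four weeks, the 3-month interview falls two months after randomization, and item 9 looks back two weeks. The common interviews therefore contain no answers given during the intervention and cannot by themselves show harm arising then. The DSMB must see both displays.

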#### Period and Frequency for Event Assessment and Follow-Up

Unanticipated problems will be recorded in the data collection system throughout the study.

The PI will record all reportable events with start dates occurring any time after informed consent is obtained until 7 (for non-serious AEs) or 30 days (for SAEs) after the last day of study participation. At each study visit, the investigator will inquire about the occurrence of AE/SAEs since the last visit. Events will be followed for outcome information until resolution or stabilization.

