## **7. Data Collection**

### **7.a. BLUE CORAL data collection**

BLUE CORAL includes data collection from enrolled patients' clinical records. There are three types of forms for each study: admission (hospital / study day 1), daily, and discharge.

The case report form (CRF) is built in REDcap which can be imported as a local instance or centrally through the PETAL CCC. Since there may be times when study personnel are mandated to work from

home due to the ongoing pandemic, BLUE CORAL has many study procedures that are designed to allow off-site completion. All elements that contribute to the COVID ordinal outcome scale are included in daily and summative data collection. Manual data entry of all elements into REDCap may not be required depending on the site's ability to extract data from the EMR.

The BLUE CORAL study will obtain pre-hospital information from patients or their caregivers before hospital discharge. The survey consists of questions regarding functional status and health-related quality of life. PETAL study staff members are familiar with the conduct of these surveys as they were used successfully in the ROSE RCT. With high severity of illness, infection control precautions, and absence of family visitation, we anticipate that survey completion will be difficult. Therefore, we have developed multiple approaches to survey completion (telephone, tablet computer, or email with either patients or families) and will attempt to complete as able.

BLUE CORAL patients who survive hospitalization, speak English, are domiciled, and did not have severe dementia or severe disability before hospitalization may be eligible to enter the post-hospital follow-up study (BLUE CORAL). This study will be conducted by the FUNCTION team at the University of Michigan, led by [name], using protocols developed and executed in the PETAL Network ROSE and ongoing CLOVERS studies. Sister sites, Oregon Health & Sciences University (OHSU) and University of Colorado-Denver, led by Drs. [name] and [name], respectively, may be asked to conduct the study visits as needed. Post-hospital follow-up will occur by telephone at 1, 3 and 6 months after hospital discharge (Table 1). Patients will provide consent for continued involvement at the time of the first call.

Table 1: Data collection timing and content for BLUE CORAL and LIFT RCT participants.					
	Hospital	1 month* (T1)	During intervention 	3 months* (T2)	6 months* (T3)
Contact info	X	X		X	X

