PHQ-9 depression (primary outcome)		X	X	X	X
GAD-7 anxiety		X		X	X
EQ-5DL quality of life	X	X		X	X
ADL / IADL limitations	X	X		X	X
Financial strain	X	X		X	X
Cardiopulmonary symptoms		X		X	X
Cognitive function (MOCA/AD8, Hayling)		X		X	X
Rehospitalization		X		X	X

\* Timing is from the time of hospital discharge  
1 Collected via the Lift mobile app weekly  
2 These data collected only for LIFT RCT participants. This will be done via the app platform.

These post-hospital assessments will allow BLUE CORAL to measure the levels and rates of recovery on cardio-pulmonary symptoms as well as the key domains outlined in the NHLBI R24-funded “Improving Long-Term Outcomes” Program; to determine risk factors associated with poor outcomes; to assess the burden of COVID-19 recovery primary spouse or family caregiver of cohort members, stratified by whether the spouse themselves had COVID-19 or not; and to evaluate the association of the COVID-19 Outcome Score with patient- centered outcomes.

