#### Post-hospital patient surveys

[figure not shown]
- COVID-19 Recovery (1 item)
- EQ-5D-5L (5 items)
- Activities of Daily Living (ADLs) and Instrumental ADLs (13 items)
- Financial Toxicity (12 items)
- Cardiopulmonary symptoms and respiratory support (13 items)
- Patient Health Questionnaire-9 (9 items)
- Generalized Anxiety Disorder-7 (7 items)
- Healthcare utilization (1 item)
- Demographics (2 items)
- Montreal Cognitive Assessment MOCA-Blind
- Hayling Test of Executive Function
- Select Current Medications, matched to those collected in-hospital

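### The one symptom named as an adverse event is assessed six times after randomization in the LIFT arm but twice in controls, and no listed instrument asks either arm about a suicide attempt

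*Combined protocol and SAP*

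**What the plan says.** **Who asks.** Section 15, under Period and Frequency for Event Assessment and Follow-Up, states: "At each study visit, the investigator will inquire about the occurrence of AE/SAEs since the last visit". Section 3 says that the University of Michigan "will screen participants, conduct informed consent, and conduct all follow up interviews". Section 7.a adds: "Post-hospital follow-up will occur by telephone at 1, 3 and 6 months after hospital discharge". It names two sister sites as back-up.

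**What counts.** Section 15 treats PHQ-9 item 9 as an AE when the answer is one of the two highest frequencies over the past two weeks. For serious events it says: "A SAE in this trial would include a suicide attempt, a hospitalization, or death".

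**What is collected.** Table 1 schedules the PHQ-9 at T1, T2 and T3, and has a row for "Rehospitalization" at the same times. Section 7.b adds a weekly in-app PHQ-9 over the 4-week intervention, for the LIFT arm only. Neither Table 1 nor the survey list in Section 7.c shows an AE question or a suicide-attempt question.

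**How it is used.** Section 17 makes AE reports and PHQ-9 scores the DSMB's main safety measures. It allows formal tests of AE rates between groups on request. The wording there refers to factor-based groups, as in the parent factorial trial. In this two-arm trial I read it as LIFT versus control.

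**The concern.** An AE that is defined by a questionnaire answer can be recorded only when the questionnaire is given. If one arm is asked three times as often, it will tend to accumulate more recorded events even when the intervention does nothing. The bias runs against LIFT. It also works the other way: a real excess in the LIFT arm could be dismissed as the result of more frequent asking. A DSMB table that pools app and telephone events cannot separate the two explanations.

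The second, smaller matter is who asks and with what words. The general AE inquiry is given to the investigator, but the scheduled contacts are calls by FUNCTION staff working from listed surveys. A suicide attempt is one of the three serious events that the protocol names, and it has no listed question.

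**Working it through.** The plan gives no figure for AE frequency or ascertainment, so there is none to reproduce. Its power calculation is not affected.

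**1. Count the assessments of item 9 after randomization.**
- LIFT: 4 weekly in-app surveys (Section 7.b, one per week for 4 weeks) + T2 + T3 = 6.
- Control: T2 + T3 = 2.
- Ratio of opportunities: 6/2 = 3.

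T1 is the baseline, and suicidal ideation at T1 is an exclusion criterion (Section 4.b). The T1 assessment therefore adds no events to either arm.

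**2. Convert the counts to participants with at least one AE, with no true difference.** Assume the same chance q at every assessment in both arms, independence between assessments, full completion, and recording of every qualifying answer as an AE. Then P(at least one) = 1 − (1 − q)^k, with k = 6 for LIFT and k = 2 for control.

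| q | Control, k = 2 | LIFT, k = 6 | Ratio |
|---|---|---|---|
| 1% | 2.0% | 5.9% | 2.9 |
| 2% | 4.0% | 11.4% | 2.9 |
| 5% | 9.8% | 26.5% | 2.7 |

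At q = 2% and 150 per arm, the expected counts are 150 × 0.1142 = 17.1 in LIFT and 150 × 0.0396 = 5.9 in controls.

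**3. Could this show up in a formal test?** At q = 2% the expected difference is 0.1142 − 0.0396 = 0.0746. The pooled proportion is 0.0769, so the standard error is √(0.0769 × 0.9231 × 2/150) = 0.0308, and z = 0.0746/0.0308 = 2.4. That exceeds 1.96 with no true effect. It assumes all 300 participants have complete data, so an interim review would have less.

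**4. How far do the assumptions matter?**
- Incomplete app use: with 2 of the 4 weekly surveys completed, k = 4 for LIFT and 1 − 0.98^4 = 7.8%. The ratio is 7.8/4.0, about 2.0.
- Persistence: if ideation were fully persistent within a person, every assessment would give the same answer and the ratio would fall to 1. Partial persistence lies between 1 and the tabled values.

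**5. Restrict the comparison to T2 and T3.** Now k = 2 in both arms. At q = 2% both give 4.0% and the ratio is 1. The artefact disappears whatever the value of q.

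**6. Set the named events beside the listed routes.**
- Item 9 ideation: PHQ-9 at T2 and T3, both arms.
- Hospitalization: the rehospitalization row of Table 1 and the healthcare-utilization item in Section 7.c, both arms.
- Death: Section 15 describes a scripted approach to vital status when a relative answers the call, both arms.
- Suicide attempt: no listed item in either arm. One that leads to neither admission nor death, and is not disclosed after an item 9 response, has no listed prompt.

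**The case against.** The strongest reply is that the protocol already states that events since the last visit will be asked about, and that a survey list is weak evidence to the contrary. Section 16.b places AE recording in a separate workflow application. Manuals of Operation and a DSMB charter are mentioned but are not available here. The lists are visibly incomplete: the PTSS, a secondary outcome, is in neither. Section 15 names Michigan investigators among those monitoring the trial, has staff watch for distress during any interview, promises alert values for all groups, and gives every participant 24-hour access to an investigator's telephone.

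Much of that stands. It limits the second part of the point to an inquiry that is not assigned to the people who make the calls and has no listed wording. It does not show that the question will go unasked.

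It does not answer the first part. The 6-to-2 imbalance arises when the plan is followed exactly. The DSMB's other main measure, the PHQ-9 score, is available on a common schedule at T2 and T3. That helps with mean symptom levels but does not repair an AE table that includes app-detected events.

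**Conclusion.** The point holds: the named AE is ascertained unequally by design. Under independence and full completion the false ratio is 2.7 to 2.9 for per-assessment chances of 1% to 5%. It is smaller with incomplete app use or persistent ideation. The values of q are assumptions, because the documents give no event rate. The gap for suicide attempts is real but narrow, and it applies to both arms.

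Three stronger readings are not supported:
- A reader might infer that AEs in controls would surface only by chance. Item 9 ideation, hospitalization and death have routes in both arms, and Section 15 adds escalation and call-back.
- A reader might infer that only about 18% of control follow-up is covered (two 2-week windows in about 21.7 weeks, 4/21.7). That describes item 9's recall period alone. The general inquiry covers the whole interval since the last visit.
- A reader might infer a broken commitment because recording runs "until 7 (for non-serious AEs) or 30 days (for SAEs) after the last day of study participation" and no call follows T3. That text sets a recording window and promises no scheduled contact.

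This is an inexpensive improvement to make. It does not undermine the primary efficacy analysis.

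**What to change.** 1. In Section 17, state that the between-arm AE comparison uses events ascertained at the common T2 and T3 assessments. List app-detected events separately, for the LIFT arm only, without a between-arm test.
2. In Section 15, reword the inquiry so that it names the telephone interviewer (FUNCTION staff or the back-up sites) as the person who asks.
3. Add to Table 1 and Section 7.c a short scripted AE/SAE prompt, including any suicide attempt since the last call. Ask it in the same words at T2 and T3 in both arms.
4. State that positive answers go to the coordinating center on the timeline already set under Reporting for Multi-Center Trials.

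The cost is protocol wording and an estimated 1 to 2 minutes on each of two calls already scheduled. Somewhat more events will be recorded. No visit is added, and sample size and power do not change.
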